### 7.3. Exploratory Endpoints and Analyses

Efficacy will be evaluated for the Phase 1b MAD portion of the study as an exploratory endpoints and details are noted throughout sections 7.1 and 7.2. Exploratory endpoints and analyses may be included in relation to the Phase 2 POC part of the study as described within this section.

Sponsor: Boston Pharmaceuticals, Inc.  
Protocol Number: BOS161721-02  
SAP Version and Date: Version 4.0, 23Apr2021

### 7.3.1. CCI [REDACTED]

CCI [REDACTED]

CCI [REDACTED]

CCI [REDACTED]

CCI [REDACTED]

## 8. PHARMACOKINETICS/PHARMACODYNAMICS/IMMUNOGENICITY

Pharmacokinetics, pharmacodynamics, and immunogenicity are secondary endpoints for the Phase 1b MAD study and exploratory endpoints for the Phase 2 POC study.

PD results reported as less than the lower limit of quantification (LLOQ) will be counted as 0.5\*LLOQ to calculate summary linear statistics and will be reported as <LLOQ in listings. All observed Immunogenicity and PD data, as provided by an external vendor, will be presented in by-patient listings.

SAPs describing analyses (pharmacokinetics [PK], PK/pharmacodynamics[PD], etc.) not covered within this SAP will be included within an Appendix of this document. The author, finalization date, signatories, and page numbering of this SAP are independent of those SAPs and vice versa. Only the last final versions will be included in the appendix just prior to study conclusion.

## 8.1. Pharmacokinetics

BOS161721 PK concentration and parameter analyses will be performed by a separate PK vendor and described under a separate SAP.

## 8.2. Pharmacodynamics

Descriptive statistics for the observed results of the following PD endpoints/results will be summarized separately at baseline and each visit. Change from baseline and percentage change from baseline will be summarized at each post-baseline visit. In cases where both numeric and qualitative results are provided, the summaries will be based on the numeric results. In cases where only qualitative results are provided and results given only as titers, shifts will be summarized. Graphical presentations of mean and SD of the change from baseline over time will also be presented for the parameters in table 6.

**Table 6**

| PD Endpoint            | Applicable Study Portion(s) | Parameters to be Included in Summary Tables and Figures ('NA (all)' is displayed if all collected parameters are to be included) |
|-------------------------------|------------------------------------|---|
| Clinical PD Biomarkers |                                    |   |
| CCI [REDACTED]                | MAD and POC                        | NA (all)  |
| C-Reactive Protein            | MAD and POC                        | NA (all)  |
| CCI [REDACTED]                | MAD and POC                        | NA (all)  |
| CCI [REDACTED]                | MAD and POC                        | NA (all)  |
| CCI [REDACTED]                | MAD and POC                        | NA (all)  |
| CCI [REDACTED]                | MAD and POC                        | NA (all)  |
| CCI [REDACTED]                | MAD and POC                        | NA (all)  |
| CCI [REDACTED]                | MAD and POC                        | NA (all)  |

Sponsor: Boston Pharmaceuticals, Inc.  
 Protocol Number: BOS161721-02  
 SAP Version and Date: Version 4.0, 23Apr2021

| PD Endpoint  | Applicable Study Portion(s) | Parameters to be Included in Summary Tables and Figures ('NA (all)' is displayed if all collected parameters are to be included)  |
|--|-----------------------------|---|
| Other Biomarkers  |                             |   |
| Phosphorylated signal transducer and activator of transcription 3 (pSTAT3) | MAD only                    | % pSTAT3+ Lymphocytes –Stimulated; Ratio MEF (Stimulated / Unstimulated)  |
| Leukocyte immunophenotype (B and NK Cells)                                 | MAD only                    | CD19+% of CD45+ Lymphocytes; IgD+C27-% of CD19+; IgD+CD27-CD38++CD24+++% of CD19+; IgD-CD27-% of CD19+; IgD+CD27+% of CD19+; IgD-CD27+% of CD19+; IgD-CD27+CD38++CD138-% of CD19+; IgD-CD27+CD38++CD138+% of CD19+; CD56+% OF CD45+ Lymphocytes |
| Leukocyte immunophenotype (T-Cells)  | MAD only                    | CD4+CD8-% of CD3+; CXCR5+% of CD4+CD8-; PD-1+% of CD4+CD8-; ICOS+% of CD4+CD8-; CD25+CD127-% of CD4+CD8-; CXCR5+% of CD25+CD127-; PD-1+% of CD25+CD127-; ICOS+% of CD25+CD127-; CD8+CD4-% of CD3+   |
| CCI [REDACTED]   | MAD only                    | CCI [REDACTED]  |
| CCI [REDACTED]   | MAD and POC                 | CCI [REDACTED]  |

| PD Endpoint    | Applicable Study Portion(s) | Parameters to be Included in Summary Tables and Figures ('NA (all)' is displayed if all collected parameters are to be included) |
|----------------|-----------------------------|--|
| CCI [REDACTED] | MAD                         | NA (all) – Listing only  |
| CCI [REDACTED] | MAD and POC                 | NA (all) – Listing only (including fold change)  |
| CCI [REDACTED] |                             |  |
| CCI [REDACTED] |                             |  |
| CCI [REDACTED] |                             |  |

Additional PD results may be plotted over time by treatment group and visit.

### 8.3. Immunogenicity

Immunogenicity data as collected on the eCRF will be provided in by-patient data listings including neutralizing antibodies (NAb) and ADA for all relevant timepoints.

All serum ADA samples that are confirmed positive in the ADA assay will be analyzed for the presence of NAb.

The proportion of patients with positive or negative ADA will be summarized by study phase, treatment group, and overall, at baseline (pre-dose), and post-baseline in the FAS. The frequency and percentage of patients with transient positive and persistent positive ADA will also be included in the summary. If warranted based on data, treatment-emergent transient positive and treatment-emergent persistent positive ADA will be summarized. The frequency and percentage of patients with confirmed positive, treatment-emergent confirmed positive, and negative ADA at each post-baseline timepoint will also be summarized. ADA designations and denominators are defined in table 7.

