## 2. STUDY OBJECTIVES AND ENDPOINTS

### 2.1. Multiple Ascending Dose (MAD) Phase 1b Study

| Objectives   | Endpoints   |
|--|---|
| 
Primary
 

To assess safety, tolerability, and immunogenicity of repeat doses of BOS161721 (20, 60, and 120 mg) administered subcutaneously (SC) in adult patients with moderately to severely active SLE on limited background standard of care treatment, in order to estimate the optimal dose.

 | 
Safety Endpoints
 

Incidence and severity of adverse events (AEs) and serious adverse events (SAEs), related AEs, AEs leading to study drug discontinuation, AEs by severity and relatedness

Injection site reactions

Columbia Suicide Severity Rating Scale (C-SSRS)

12-lead electrocardiograms (ECGs) parameter results at each visit and change from baseline

Vital signs (blood pressure [BP], heart rate, and temperature) parameter results at each visit and change from baseline

Clinical laboratory results and change from baseline

Physical examinations changes from baseline

Anti-drug antibodies (ADAs)

Study drug exposure/compliance

 |

| Objectives  | Endpoints   |
|-------------|---|
| Secondary   | 
Pharmacokinetic (PK) Endpoints
 
 
• BOS161721 concentration by visit and time point
 
• Maximum observed concentration (<math>C_{max}</math>), first time to maximum concentration (<math>T_{max}</math>), area under the concentration-time curve (AUC), terminal half-life (<math>t_{1/2}</math>), systematic clearance (<math>Cl</math>), volume of distribution (<math>V_d</math>)
 
 
Pharmacodynamic (PD) Endpoints
 
 
• Results and changes (or shifts) from baseline to each visit in phosphorylated signal transducer and activator of transcription 3 (pSTAT3), C3 and C4 levels, and leukocyte immunophenotype
 
• Results and changes (or shifts) from baseline in anti-double-stranded DNA (dsDNA), antinuclear antibodies (ANA), anti-Sjögren syndrome A and B (SSA, SSB), Smith (Sm), and antiphospholipid (APL) autoantibodies at each visit
 
• Results and changes (or shifts) from baseline in abrogation of IL-21 gene signature at each indicated visit
 
 |
| Exploratory | 
 
• CCI
 
    |

Sponsor: Boston Pharmaceuticals, Inc

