### 3.3. Sample Size Considerations

Sample size in the Phase 1b part of the study is based on operational consideration.

The sample size in the Phase 2 POC study is based on the primary endpoint, SRI-4 Response at Day 210. Based on efficacy data from a recently completed study with Ustekinumabiii, where the primary endpoint was also SRI-4, the sample size in the phase 2 part of the BOS161721-02 study is set at 96 evaluable patients. In the Ustekinumab study of 102 patients, a statistically significant difference in SRI-4 response was shown in favor of Ustekinumab (62% of Ustekinumab treated patients achieved SRI-4 response vs. 33% in patients receiving placebo). The Ustekinumab phase 2 study is an appropriate comparator to BOS161721-02 because both studies share the same primary endpoint of SRI-4 response and BOS161721 and Ustekinumab have overlapping mechanisms of action (T follicular helper and Th17 cell biology).

Sponsor: Boston Pharmaceuticals, Inc.  
Protocol Number: BOS161721-02  
SAP Version and Date: Version 4.0, 23Apr2021

Approximately 110 additional patients will be randomized in a 2:1 ratio to BOS161721 versus placebo to achieve approximately 96 evaluable patients in the FAS of the phase 2 portion. This assumes 14 patients will discontinue prior to having received treatment or having completed a post-baseline efficacy measure. Enrollment and randomization will be monitored in a blinded fashion and may be increased if needed to ensure at least 96 evaluable patients are randomized into the FAS (see Section 6.1).

A total of 96 evaluable patients randomized provides 80% power to detect a treatment difference of 29% in SRI-4 response rates at Day 210, based on a targeted 2-sided significance level of 10% and using a 2-sided Pearson's chi-squared test. This assumes a response rate of 62% for BOS161721 and 33% for placebo.

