# 6. STUDY PATIENT DATA

## 6.1. Analysis Populations/Sets

**FAS:** Defined as all patients who receive at least one dose (partial or complete) of study treatment and have at least one evaluable post-baseline efficacy evaluation (BILAG, PGA,

Sponsor: Boston Pharmaceuticals, Inc.  
Protocol Number: BOS161721-02  
SAP Version and Date: Version 4.0, 23Apr2021

SLEDAI-2K, CLASI, ACR-28, SLICC/ACR, **CCI** [REDACTED], or **CCI** [REDACTED]). FAS analyses will be conducted on the basis of the assigned (randomized) treatment. The FAS will be used as the basis for the primary efficacy analysis.

**Safety Analysis Set (SS):** Defined as all patients who receive at least one dose (partial or complete) of study treatment and have at least one evaluable post-baseline safety evaluation (adverse events, concomitant medications, vital signs, physical examination, ECG, or laboratory assessment). Safety analyses will be conducted on the basis of actual treatment received as reported on the eCRF. The SS will be the basis of all safety reporting.

**Per Protocol Set (PP):** Defined as all patients from the FAS except those with major deviations to the protocol deemed to impact the analysis of the primary endpoint. These deviations will be identified based on blinded data review prior to study unblinding. Patients with more than one missed dose and patients with both Day 180 and Day 210 efficacy assessments (BILAG, SLEDAI-2K, or PGA) missing will be excluded from the PP. PP analyses will be conducted on the basis of the assigned (randomized) treatment. Additional information on inclusion into this population can be found in Section 6.3.

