|                                 | Treatment-Emergent | 
Scenario 1:
 
(1) Negative ADA at baseline
 
(2) Confirmed positive ADA at the post-baseline timepoint
 
Scenario 2:
 
(1) Confirmed positive ADA at baseline
  |   |

|         |          |  |  |
|---------|----------|--|--|
|         |          | (2) Confirmed positive ADA at the post-baseline timepoint and the titer at the of the confirmed positive ADA is $\geq 4$ times greater than the baseline titer |  |
|         | Negative | Negative ADA at the post-baseline timepoint  |  |
| Overall | Positive | A patient with positive baseline (pre-dose) ADA or positive post-baseline ADA  | Number of patients with a baseline or post-baseline ADA assessment |
|         | Negative | A patient with negative baseline (pre-dose) ADA and negative post-baseline ADA at all time points  |  |

The frequency and percentages of positive and negative neutralizing antibodies will be summarized in the FAS overall and at each relevant post-baseline timepoint (i.e., Day 15, Day 30, Day 60, Day 90, Day 180, Day 270). The denominators will be the number of patients with non-missing NAb data overall and at each timepoint, respectively.

The adverse event overview table from section 10.1 will be repeated by post-baseline positive and negative ADA as defined in table 7 in the safety analysis set. Additional adverse event analyses may be performed by post-baseline transient positive and persistent positive.

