## 10. SAFETY

All safety analysis reporting will be based on the Safety Analysis Set. Unless otherwise noted, all safety analyses will be presented overall, by study phase, and treatment group.

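### Anti-drug antibodies are a safety endpoint, yet SAP Section 8.3 tabulates them in the FAS as randomised rather than in the Safety Set by treatment received

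*SAP*

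**What the plan says.** **Status of the endpoint.** Sections 2.1 (Phase 1b) and 2.2 (Phase 2) both place ADA under Safety Endpoints. The Phase 1b primary objective names immunogenicity alongside safety and tolerability. Section 8 opens with a different label: "Pharmacokinetics, pharmacodynamics, and immunogenicity are secondary endpoints for the Phase 1b MAD study and exploratory endpoints for the Phase 2 POC study".

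**General rule for safety.** Section 6.1: "The SS will be the basis of all safety reporting". Patients in that set are counted under the treatment they actually received. Section 10 repeats the rule: "All safety analysis reporting will be based on the Safety Analysis Set".

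**Set used for antibodies.** Section 8.3 fixes the set for the ADA frequencies thus: "positive or negative ADA will be summarized by study phase, treatment group, and overall, at baseline (pre-dose), and post-baseline in the FAS". The NAb frequencies, described after Table 7, are also in the FAS. Under Section 6.1 the FAS requires one dose plus at least one evaluable post-baseline efficacy evaluation, and its analyses follow the randomised assignment.

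**Set used for the linked table.** The last paragraph of Section 8.3 repeats the adverse event overview by post-baseline ADA status. It uses the Table 7 definitions but the Safety Set.

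**The concern.** An antibody result does not depend on a lupus activity score, and the SAP gives no reason for making its tabulation conditional on one. Two things follow from using the FAS.

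- A treated patient who gives an antibody sample but has no evaluable efficacy evaluation is left out of the ADA and NAb frequency tables.
- Anyone who received the other treatment by mistake is shown under the assigned arm. A patient randomised to placebo but given BOS161721 who formed antibodies would appear as a placebo positive.

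Section 8.3 then uses the other set for the table that relates ADA status to adverse events. A reader of the study report could find two ADA-positive counts for one arm, with nothing in the plan to explain the difference. This matters most in Phase 1b, where immunogenicity is in the primary objective and the cohorts are very small.

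**Working it through.** **1. The two sets side by side (Section 6.1)**

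| | FAS | Safety Set |
|---|---|---|
| Dosing | at least one dose | at least one dose |
| Further condition | one evaluable post-baseline efficacy evaluation | one evaluable post-baseline safety evaluation |
| Arm | as randomised | as received |
| Used in Section 8.3 for | ADA and NAb frequencies | adverse events by ADA status |

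The sets differ in membership and in arm. A patient who returned for an antibody sample would be expected to meet the safety condition, so moving to the Safety Set should mainly add patients.

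**2. Who is affected.** Those who are treated, have no evaluable post-baseline efficacy evaluation, and have the ADA sample that the Table 7 row requires. For the post-baseline rows this is a post-baseline sample; for the overall row a baseline sample is enough.

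**3. Phase 2, upper and lower bound.** Section 3.3 plans about 110 randomised at 2:1 and 96 evaluable in the FAS. The difference is explained thus: "This assumes 14 patients will discontinue prior to having received treatment or having completed a post-baseline efficacy measure".

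- Planned losses: 110 − 96 = 14, which matches; 14/110 = 12.7%.
- Active arm: 110 × 2/3 = 73.3 randomised and 96 × 2/3 = 64 in the FAS; gap 9.3.
- Placebo arm: 110 × 1/3 = 36.7 randomised and 96 × 1/3 = 32 in the FAS; gap 4.7.

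The 14 combine never-treated patients, who belong to neither set, with treated patients lacking an efficacy measure. The SAP gives no split. On the planning assumption the number affected is therefore 0 to 14, of whom 0 to about 9 are on active drug if losses follow 2:1. It is smaller still once an antibody sample is required. (The 96 itself reproduces as 32 + 64 with the continuity-corrected two-proportion formula for 33% versus 62%, two-sided 10% level, 80% power. Nothing here depends on it.)

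**4. Phase 1b.** Section 3.1.1 gives 5 active patients in Cohort 1 and 9 in each of Cohorts 2 and 3. One affected active patient is 1/5 = 20% of Cohort 1, or 1/9 = 11% of Cohort 2 or 3.

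**5. Possible effect on a Phase 2 rate (illustration).** Assume 6 of the 64 active FAS patients are ADA-positive: 6/64 = 9.4%. Let *m* further treated active patients with a sample be added. The Safety Set rate then lies between 6/(64 + *m*), if none of them is positive, and (6 + *m*)/(64 + *m*), if all are.

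| *m* | None positive | All positive |
|---|---|---|
| 0 | 9.4% | 9.4% |
| 3 | 6/67 = 9.0% | 9/67 = 13.4% |
| 9 | 6/73 = 8.2% | 15/73 = 20.5% |

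The 6 and the values of *m* are assumptions; the SAP gives neither.

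**6. The endpoint label.** Section 8 calls immunogenicity secondary in Phase 1b and exploratory in Phase 2. Section 2.1 shows only PK and PD as Phase 1b secondary endpoints, and Section 7.2 likewise names only those two. The exploratory lists are redacted, but the listing of ADA as a safety endpoint is legible in both phases, so the label in Section 8 conflicts with it.

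**The case against.** Section 8 could be offered as the justification: if immunogenicity is secondary or exploratory, it need not follow the safety rule. This does not stand. The label contradicts Sections 2.1 and 2.2, and even a secondary endpoint would not call for an efficacy evaluation before an antibody result is counted.

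The objections to the consequence are stronger, and most of them hold. A reader might infer the following from the wording of Section 8.3.

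- *That antibody results are lost.* They are not. Sections 8 and 8.3 provide by-patient listings of the immunogenicity data, and the adverse event table by ADA status covers the Safety Set. Only the frequency tables omit these patients.
- *That anyone stopping after the first dose drops out.* The first NAb timepoint is Day 15 and the SRI listing begins at Day 30, but neither is the efficacy schedule, which is in the protocol. Any one of several instruments admits a patient to the FAS. Section 7.1.1 (Out of Window Assessments) records Day 180 jointly with End of Treatment and guards against assessments made too early to count as Day 180. Early stoppers may therefore well have an efficacy assessment at that visit.
- *That about 9 active patients will be missing.* That is the upper end of a range that starts at 0.
- *That those removed are the patients who reacted to the drug.* Leaving the FAS depends on a missing efficacy evaluation. Nothing in the SAP ties that to a reaction.
- *That the two tables could never be reconciled.* Section 6.2 reports the size of each analysis set and the listings identify each patient, so a difference could be traced. Wrong attribution also needs a dosing error, and the document reports none.
- *That the NAb denominator is an error.* Section 8.3 states "All serum ADA samples that are confirmed positive in the ADA assay will be analyzed for the presence of NAb", and for the percentages "The denominators will be the number of patients with non-missing NAb data overall and at each timepoint, respectively". Read together, these probably give the share among ADA-positive patients rather than incidence among those assessed. The denominator is openly stated, and ADA incidence is tabulated separately, so this is a matter of presentation.

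**Conclusion.** The inconsistency is established from the SAP alone. A listed safety endpoint, part of the Phase 1b primary objective, is tabulated in an efficacy set as randomised, against the rule in Sections 6.1 and 10. It is also at odds with the set used for the adverse event table in the same section, and Section 8 mislabels the endpoint.

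The numerical consequence is unknown and may be nil. It is bounded by 0 to 14 patients in Phase 2 (0 to about 9 active) if the planned losses and 2:1 allocation hold. In Phase 1b each affected active patient is 20% or 11% of a cohort. The effect is confined to the ADA and NAb frequency tables and to the agreement between tables. Sample size and power do not change. The correction should be made because it is simple and removes an irrelevant condition from a safety summary, not because a material bias has been shown.

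**What to change.** - In Section 8.3, for the ADA and NAb summaries, replace the reference to the FAS with *the Safety Analysis Set, by treatment actually received*. Keep the Table 7 denominators.
- In Section 8, align the status of immunogenicity with Sections 2.1 and 2.2: a safety endpoint in both phases, and part of the primary objective in Phase 1b.
- Optional, for presentation only: label the NAb percentage as the share among patients with NAb results, and add a line over patients with a post-baseline ADA assessment.

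The cost is SAP wording and a change of population flag in the ADA and NAb programs. ADA status must already be derived for the Safety Set to produce the adverse event table, so the change needs no new data.

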**Table 7**

| Timepoint                 | ADA Designations | Definition                         | Denominator/Evaluable Patients                      |
|---------------------------|------------------|------------------------------------|---|
| Baseline (Day 0 Pre-Dose) | Positive         | Confirmed positive ADA at baseline | Number of patients with a baseline and at least one |

Sponsor: Boston Pharmaceuticals, Inc.  
 Protocol Number: BOS161721-02  
 SAP Version and Date: Version 4.0, 23Apr2021

|               |                                   |  |   |
|---------------|-----------------------------------|--|---|
|               | Negative                          | Negative ADA at baseline   | post-baseline ADA assessment                                      |
| Post-Baseline | Positive                          | Confirmed positive ADA at any time after baseline  | Number of patients with at least one post-baseline ADA assessment |
|               | Negative                          | Negative ADA at all times after baseline   |   |
|               | Transient Positive iv  | 
(1) Last ADA sampling timepoint is negative
 
AND 2a OR 2b:
 
(2a) Only one post-baseline confirmed positive ADA (excluding the last sampling timepoint) exists and last ADA negative sample is at least 16 weeks apart from the previous confirmed positive sample.
 
OR
 
(2b) Two or more post-baseline confirmed positive ADA where the first and last ADA confirmed positive samples are less than 16 weeks apart (irrespective of any negative ADA in between) and last ADA negative sample is at least 16 weeks apart from the previous confirmed positive sample.
 |   |
|               | Persistent Positive iv | 
1 OR 2 OR 3:
 
(1) Two or more post-baseline confirmed positive ADA where the first and last ADA confirmed positive samples are more than 16 weeks apart (irrespective of any negative ADA in between)
 
OR
   |   |

|                    |                                  |  |   |
|--------------------|----------------------------------|--|---|
|                    |                                  | 
(2) Confirmed positive ADA at the last post-baseline assessment
 
OR
 
(3) Negative ADA at the last post-baseline assessment and a prior confirmed positive ADA sample occurred less than 16 weeks before the last post-baseline negative ADA sample
  |   |
| Treatment-Emergent | Positive                         | 
A post-baseline confirmed positive result exists with a titer <math>\geq 4</math> times greater than the baseline titer
 
OR
 
Any post-baseline confirmed positive result after a negative baseline result
 
Note: The number of treatment-emergent transient positive and treatment-emergent persistent positive ADA will sum to the total positive treatment-emergent ADA
 
Note: If baseline ADA data is missing, the baseline value is treated as negative for this analyses
 | Number of patients with at least one post-baseline ADA assessment |
|                    | Transient Positive iv | 
Scenario 1:
 
(1) Negative ADA at baseline
 
AND
 
(2) Last ADA sampling timepoint is negative
 
AND (3a OR 3b):
 
(3a) Only one post-baseline confirmed positive ADA (excluding the last sampling timepoint) exists and last ADA negative sample is at
   |   |

Sponsor: Boston Pharmaceuticals, Inc.

Protocol Number: BOS161721-02

SAP Version and Date: Version 4.0, 23Apr2021

|  |  |  |  |
|--|--|--|--|
|  |  | 
least 16 weeks apart from the previous confirmed positive sample.
 
OR
 
(3b) Two or more post-baseline confirmed positive ADA where the first and last ADA confirmed positive samples are less than 16 weeks apart (irrespective of any negative ADA in between) and last ADA negative sample is at least 16 weeks apart from the previous confirmed positive sample.
 
Scenario 2:
 
(1) Confirmed positive ADA at baseline
 
AND
 
(2) Last ADA sampling timepoint is negative or is the same as baseline ADA levels
 
AND (3a OR 3b):
 
(3a) Only one post-baseline confirmed positive ADA (excluding the last sampling timepoint) exists and the titer at the post-baseline timepoint is <math>\geq 4</math> times greater than the baseline titer
 
OR
 
(3b) Two or more post-baseline confirmed positive ADA where the first and last ADA confirmed positive samples are less than 16 weeks apart (irrespective of any negative ADA in between) and the titers at each of the two or more post-baseline confirmed positive
 |  |
|--|--|--|--|

Sponsor: Boston Pharmaceuticals, Inc.

Protocol Number: BOS161721-02

SAP Version and Date: Version 4.0, 23Apr2021

|  |                                   |   |  |
|--|-----------------------------------|---|--|
|  |                                   | 
timepoints are <math>\geq 4</math> times greater than the baseline titer
 
Note: If baseline ADA data is missing, the baseline value is treated as negative for this analyses
   |  |
|  | Persistent Positive iv | 
Scenario 1:
 
(1) Negative ADA at baseline
 
AND (2 OR 3 OR 4):
 
(2) Two or more post-baseline confirmed positive ADA where the first and last ADA confirmed positive samples are more than 16 weeks apart (irrespective of any negative ADA in between)
 
OR
 
(3) Confirmed positive ADA at the last post-baseline assessment
 
OR
 
(4) Negative ADA at the last post-baseline assessment and a prior confirmed positive ADA sample occurred less than 16 weeks before the last post-baseline negative ADA sample
 
Scenario 2:
 
(1) Confirmed positive ADA at baseline
 
AND (2 OR 3 OR 4):
 
(2) Two or more post-baseline confirmed positive ADA where the first and last ADA confirmed positive samples are more than 16 weeks apart (irrespective of any negative ADA in between) and the
 |  |

Sponsor: Boston Pharmaceuticals, Inc.

Protocol Number: BOS161721-02

SAP Version and Date: Version 4.0, 23Apr2021

|                                 |                    |   |   |
|---------------------------------|--------------------|---|---|
|                                 |                    | 
titors at each of the two or more post-baseline confirmed positive timepoints are <math>\geq 4</math> times greater than the baseline titer
 
OR
 
(3) Confirmed positive ADA at the last post-baseline assessment and the titer at the last post-baseline timepoint is <math>\geq 4</math> times greater than the baseline titer
 
OR
 
(4) Negative/similar to baseline ADA at the last post-baseline assessment and a prior confirmed positive ADA sample occurred less than 16 weeks before the last post-baseline negative/similar to baseline ADA sample and the titer of the confirmed positive ADA is <math>\geq 4</math> times greater than the baseline titer
 
Note: If baseline ADA data is missing, the baseline value is treated as negative for this analyses
 |   |
| Post-baseline at each timepoint | Positive           | Confirmed Positive ADA at the post-baseline timepoint   | Number of patients with ADA assessment at baseline and at the post-baseline timepoint |
|                                 | Treatment-Emergent | 
Scenario 1:
 
(1) Negative ADA at baseline
 
(2) Confirmed positive ADA at the post-baseline timepoint
 
Scenario 2:
 
(1) Confirmed positive ADA at baseline
  |   |

|         |          |  |  |
|---------|----------|--|--|
|         |          | (2) Confirmed positive ADA at the post-baseline timepoint and the titer at the of the confirmed positive ADA is $\geq 4$ times greater than the baseline titer |  |
|         | Negative | Negative ADA at the post-baseline timepoint  |  |
| Overall | Positive | A patient with positive baseline (pre-dose) ADA or positive post-baseline ADA  | Number of patients with a baseline or post-baseline ADA assessment |
|         | Negative | A patient with negative baseline (pre-dose) ADA and negative post-baseline ADA at all time points  |  |

The frequency and percentages of positive and negative neutralizing antibodies will be summarized in the FAS overall and at each relevant post-baseline timepoint (i.e., Day 15, Day 30, Day 60, Day 90, Day 180, Day 270). The denominators will be the number of patients with non-missing NAb data overall and at each timepoint, respectively.

The adverse event overview table from section 10.1 will be repeated by post-baseline positive and negative ADA as defined in table 7 in the safety analysis set. Additional adverse event analyses may be performed by post-baseline transient positive and persistent positive.

